Sample of Department Leadership: All Program Directors (PDs) and chairs will be mailed annually a modified version of the CSQ-8 (given successfully in a prior survey of program directors in 2011) to assess their knowledge of the RFWP and ISP initiative and satisfaction with the RFWP as a service to their trainees and faculty. The expected number surveyed will be approximately 100. The surveys will be anonymous and only aggregate, de-identified data will be presented for purposes of data analysis and publication.

SOM Summary Data

In order to conduct analyses comparing participants in the ISP surveys and participants in the RFWP to the overall Providence and Legacy trainee and OHSU SOM trainee and faculty population, some summary SOM data will be provided to the researchers by the Dean's Office and Graduate Medical Education data analyst. Specifically, deidentified, summary data will be gathered starting in 2014 annually until the end of the project. Data requested will be:

Number of residents, fellows, primary SOM faculty,

% women/men,

% ethnic/racial groups,

average age in trainee, faculty groups,

number of trainees, faculty in 5 specialty groups (primary care, hospital based, surgical, peds/IM specialty, other)

Vulnerable Populations:

There are no vulnerable populations included in this study as all residents, fellows, faculty, and department leadership are assumed to be mentally competent and able to respond to the English language survey (since they are working full-time and functioning as health professionals at OHSU).

Consent and Measures to Protect Subjects' Privacy

Per federal and state law regarding providing confidential psychological services, all residents, fellows, and faculty seen for treatment at the RFWP will complete an informed Consent to Treatment and a separate Research Study Consent.

All RFWP outcomes data included in the research study, ISP data, and department leadership surveys will be de-identified and only aggregated data reported in analyses for purposes of quality improvement and research presentations and publications. No protected health information will be included in any analyses. No genetic information is gathered in any of the protocols. Subjects who do not wish to participate in the outcomes research study through the RFWP also may decline to complete the measures of distress (ACORN), burnout (MBI screen) or client satisfaction (CSQ). In addition, to help protect research subjects' privacy, the researchers obtained a Certificate of Confidentiality for this **study data and the repository it will be stored in** from the National Institutes of Health. With this Certificate, the researchers cannot be forced to disclose information that may identify research subjects, even by a court subpoena, in any federal, state, or local civil, criminal, administrative, legislative, or other proceedings. The researchers will use the Certificate to resist any demands for information that would identify research subjects, except as explained below:

The Certificate cannot be used to resist a demand for information from personnel of the United States Government that is used for auditing or evaluation of federally funded projects or for information that must be disclosed in order to meet the requirements of the federal Food and Drug Administration (FDA). Subjects will be informed that a Certificate of Confidentiality does not prevent them or a member of their family from voluntarily releasing information about the subjects or their involvement in this research. If an insurer, employer, or other person obtains subjects' written consent to receive research information, then the researchers may not use the Certificate to withhold that information. However, if we learn about abuse of a child or elderly person or that research subjects intend to harm themselves or someone else, or about certain communicable diseases, we will report that to the proper authorities.

Compensation: Participants in the ISP or RFWP services will not be compensated for their participation. Both programs are seen as a benefit to participants in terms of increasing self-awareness and offering free resources and counseling as needed. There will be no benefit to participating in the research other

than the knowledge that they may be helping the investigators to determine how to best help other distressed health care providers.

Costs: there are no additional costs to subjects for their participation. All RFWP services are offered free of charge to eligible SOM faculty and all residents and fellows (the program is funded 100% by GME/OHSU hospital) and the Faculty Practice Plan.

Process for Withdrawing/Termination: At any point during the ISP protocol (filling out the ISP survey, dialoguing with the RFWP clinician online), ISP participants can choose to not accept referrals and withdraw from participation without any consequences. For example, even if participants report being high risk (Tier 1), they are anonymous so the RFWP clinician would not be able to identify for who they are and would simply encourage them to come in for an in-person evaluation or access crisis intervention services in the community. Numbers to community and national hotlines and urgent consultation to the RFWP staff are posted on the ISP website for OHSU participants.

In the RFWP program, participants being seen in-person or virtually (via telehealth) can withdraw from treatment and/or from the research study at any time without penalty. The RFWP is a voluntary service and does not provide mandated treatment or fitness for duty treatment/evaluations. If there are imminent concerns for the RFWP participant's safety or others' safety (e.g., patient safety), the participant is informed (in the first meeting and consent form) that the RFWP clinician may break confidentiality and communicate with the participant's family members/emergency contact and/or program director/chair to assess safety concerns. A RFWP participant may be asked to take a leave of absence and have a fitness for duty evaluation before returning to duty if there are significant concerns about their ability safely practice as a health care provider.

Statistical Analyses:

Statistical analyses will be conducted by [name] and her research team and will consist of descriptive analyses (e.g., frequencies, means, standard deviations), correlational analyses, and some multiple regression analyses to determine whether participation in the ISP is predictive of engagement in treatment and recovery from depression, substance abuse, or suicide risk. In addition, pre-post comparisons of risk, distress and burnout levels will be conducted in relation to demographic and treatment factors for all participants in the RFWP. Additional analyses will be conducted comparing participants to overall Providence and OHSU SOM populations on demographics to see if samples are representative of their institution's eligible population.

References

ACORN, Collaborative Outcomes Resource Network. <https://psychoutcomes.org>.

Accreditation Council for Graduate Medical Education. ACGME institutional requirements.

http://www.acgme.org/acgmeweb/Portals/0/irc_IRCpr07012007.pdf. Updated 2007. Accessed November 4, 2012.

American Medical Association. Physician suicide webinars. <http://www.ama-assn.org/pub/physician-resources/physician-health/physician-suicide>. Accessed 11/20/2011.

Boroff, K. E., & Lewin, D. (1997). Loyalty, Voice, and Intent to Exit a Union Firm: A Conceptual and Empirical Analysis. *Industrial and Labor Relations Review*, 51(1), 50-63.

Drum, DJ et al. New data on the nature of suicidal crises in college students: Shifting the paradigm. *Professional Psychology*. 2009; 40, 213-222.

Ey S, [name] M, Kinzie JM, Choi D, Girard DE. "If you build it, they will come": Attitudes of medical residents and fellows about seeking services in a resident wellness program. *JGME*. 2013 (Sept).

Gallagher RP. *National Survey of Counseling Center Directors*. Monograph Series Number 80. Alexandria, VA: International Association of Counseling Services. 2005.

Gaynes BN et al. Screening for suicide risk in adults: A summary of the evidence for the US preventive services task force. *Ann Intern Med*. 2004; 140: 822-835.

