4. How helpful were components of the ISP (getting feedback on level of distress, being able to dialogue with clinician re: concerns, and having specific resources offered) according to participants in the ISP who came for initial intake at RFWP?

- a. Prior ISP studies with undergraduate and graduate samples (e.g., Haas et al., 2008) would suggest that the online dialogue with a clinician re: concerns will be rated as especially helpful and instrumental to ISP participants who eventually sought treatment.
- 5. How many residents, fellows, and faculty show significant change in their levels of distress and burnout while in treatment at the RFWP? What demographic variables (gender, ethnicity), training/work variables (trainee/faculty status, type of program, year of training) are associated with change in distress and burnout ratings across treatment?
- 6. Is dose of treatment (# of sessions over 12 month period) associated with lower risk of quitting training program, leaving faculty position or leaving clinical medicine as a field?
- 7. At intake, what is the association between descriptive variables (i.e., demographics, programmatic factors), level of distress, burnout, and intent to quit medicine and/or training program or faculty position? Is dose of treatment (number of sessions over a 12 month period) associated with lower risk of quitting training program or faculty position?
 - a. Questions about intent to quit will be based on Boroff et al. measure used by employers and now being used in healthcare setting (e.g., OHSU Pulse Survey).
 - b. Status in training program, faculty position will be based upon clinician rating in last session.
- 8. How do consumers of RFWP services compare to the overall Providence, Legacy and OHSU population of trainees and SOM faculty in terms of demographics, program type? Are they representative?
 - a. Hypothesis: This first question is exploratory as little research exists on specific rates of recovery (e.g., decrease in distress) in health care providers in counseling/coaching. In general outpatient clinics, there are no gender or racial/ethnic differences in response to high quality mental health services (e.g., Lambert , 2007).
 - b. Hypothesis: the 2nd question—prior studies with a general population would suggest that women and primary care physicians, will be more likely to have sought counseling.

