and the RFWP clinician and whether he/she accepted a referral for services and expressed willingness to schedule an in-person evaluation at the RFWP. Note: no identifying information will be included in the ISP database other than gender, broad categories of year of training or faculty status, broad category of age and type of program (e.g., primary care vs. nonprimary care). If the participant reveals his/her name in any communications with the RFWP clinician, this data will be deleted from the ISP database. Appointments will be scheduled outside of the ISP system by instructing the participant to contact the RFWP clinician directly via OHSU email and at that time revealing who they are.

At the first in-person or telehealth (during modified operations under COVID-19, all RFWP visits became telehealth) appointment at the RFWP, the client will be asked to review and sign a (1.) consent form to participate in treatment at the RFWP and (2.) a research consent form. Clients may be given a copy of the research consent form to review and then be given the option to sign the research consent form in subsequent sessions. The research consent form will include wording that the client is giving permission for retrospective data (prior to signature on research consent form) to be included in the study. Due to all visits now being telehealth, the intake paperwork and research consent forms are presented and reviewed in the telehealth session and client then can complete them and email them back to the clinician via secure OHSU email.

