ISP Sample of Residents, Fellows, and Faculty: All OHSU residents and fellows (approximately 800 annually) and all full-time (0.5 FTE) faculty (approximately 3000) will be sent via OHSU email a link to the ISP survey following the RFWP clinician's presentation of the Stress and Depression workshop to their department. Note: only residents, fellows and full-time SOM faculty will be included as they are the only ones who are eligible for services through the RFWP (we don't have capacity to provide services to all adjunct faculty). All Legacy residents (approximately 90 a year) will be invited by RFWP clinicians (during workshops/orientation to these groups) to participate in completing the ISP. Note: new Legacy residents/fellows effective 7/1/21 will no longer be enrolled. All Providence residents (approximately 90 a year) will be invited by RFWP clinicians (during workshops/orientation to these groups) to participate in completing the ISP. *RFWP Client Outcomes Sample:* All patients seen at the RFWP (to start with IRB approval) will be invited to participate in the research study—estimated to be 200-300 annually that are seen at the program. This estimate is based on 17% of 800 OHSU residents/fellows and approximately 2% of 3000 SOM faculty utilizing services through the RFWP in 2012-13. Increased outreach efforts through this proposed project “Reaching Out” will likely raise the visibility of the RFWP (especially among faculty) and lead to a slightly higher number of faculty and medical trainees utilizing future RFWP annually.

All clinical data are entered into an encrypted ACCESS clinical records database that only RFWP clinicians have permission to access. Participants who also complete the Research Study Consent Form will have the following clinical data exported into a research database for analyses: RFWP Subject ID number* randomly assigned (by computer) to the resident, fellow, or faculty member at time of intake,

- demographic and work/training program information (gender, year of birth, ethnic/race, year of training if relevant, resident/faculty status, type of program/specialty) from the “Personal History and Data Form” completed by the patient in the first meeting
- reason for referral, referral source, knowledge of RFWP
- psychological, suicide, and medication history (if relevant) based on clinical interview
- participation in the ISP and ratings of helpfulness of the ISP components (in “Personal Health History and Data Form”)

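### The institutional data request gives no trainee/faculty split for gender and ethnicity, so crude client-versus-population comparisons would be confounded by role; ISP age and ethnicity also lack a usable match

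*Protocol*

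**What the plan says.** Research questions 2 and 8 ask whether ISP participants and RFWP clients resemble the eligible trainees and faculty of OHSU, Providence and Legacy. Hypothesis 8b, under Research Questions, predicts that "women and primary care physicians, will be more likely to have sought counseling".

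The reference figures come from the request in SOM Summary Data. Its first line is "Number of residents, fellows, primary SOM faculty". The next two lines ask for the percentage of women and men and the percentage in each ethnic or racial group, with no group named. The age line then reads "average age in trainee, faculty groups", and the specialty line asks for numbers of trainees and faculty in five groups.

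On the participant side, Sample and Measures records gender, year of birth, ethnicity, resident/faculty status and specialty for RFWP clients. The ISP database described under Procedures is narrower. Nothing that could identify a participant is kept there beyond a short list, which the protocol words as follows: "included in the ISP database other than gender, broad categories of year of training or faculty status, broad category of age and type of program". It therefore has no ethnicity and only banded age.

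The expected number of RFWP clients is explained in Sample and Measures: "This estimate is based on 17% of 800 OHSU residents/fellows and approximately 2% of 3000 SOM faculty utilizing services". Statistical Analyses plans "comparing participants to overall Providence and OHSU SOM populations on demographics", without mentioning Legacy.

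**The concern.** The request spells out the trainee/faculty split for age and specialty and omits it for gender and ethnicity. An analyst who fills it literally would return pooled percentages. Trainees use the programme at 17% and faculty at about 2%, so the client group is mostly trainees while the population is mostly faculty. If the two groups differ in the proportion of women or in ethnic make-up, that difference appears in the client-versus-population comparison even when nobody is selected by gender or ethnicity within either group.

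The gender half of hypothesis 8b is exposed most directly. A difference in role mix could be read as women seeking more counselling, or could hide a real effect. Recording each client's role does not help if the reference is pooled. An analysis plan can stratify the clients, but it cannot split a percentage that was supplied only in total.

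The ISP has two further gaps. Banded age has to be set against a mean, and ethnicity has nothing on the ISP side to compare.

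**Working it through.** **Inputs from Sample and Measures.** About 800 OHSU trainees and about 3000 faculty; use of 17% and about 2%; 200-300 clients a year; about 90 Legacy and about 90 Providence residents a year.

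**The protocol's own figure.** 0.17 × 800 = 136 trainees and 0.02 × 3000 = 60 faculty, total 196. This reproduces the lower end of the stated 200-300. The upper end does not follow from these rates.

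**Role mix.**
- Trainee share of clients: 136/196 = 0.694.
- Trainee share of the OHSU population: 800/3800 = 0.211.
- Difference: 0.694 − 0.211 = 0.483.

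**Size of the artefact.** Let T and F be the percentage of women among trainees and faculty, and suppose no gender selection within either group. Then

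client % − population % = [0.694T + 0.306F] − [0.211T + 0.789F] = 0.483 × (T − F).

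The same expression holds for the share of any ethnic group.

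**False-rejection rate.** The protocol gives neither T nor F, nor a test or significance level. Assume F = 40%, gaps T − F of 5, 10 and 20 points, and a two-sided 0.05 one-sample z-test of the client proportion p₁ against the pooled reference p₀. The rejection rate is Φ[(p₁ − p₀ − 1.96·SE₀)/SE₁] plus the opposite tail, with SEᵢ = √(pᵢ(1 − pᵢ)/n). With one year's n = 196:

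| Assumed gap | p₀ | p₁ | Spurious difference | False rejection |
|---|---|---|---|---|
| 5 points | 41.1% | 43.5% | 2.4 points | 11% |
| 10 points | 42.1% | 46.9% | 4.8 points | 28% |
| 20 points | 44.2% | 53.9% | 9.7 points | 78% |

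**Sensitivity.**
- *Affiliates included.* The population share becomes 980/3980 = 0.246. If affiliates also use the programme at 17% (assumed), the client share is 166.6/226.6 = 0.735. The multiplier is 0.735 − 0.246 = 0.489, almost unchanged.
- *More faculty clients.* If clients reached 300 and every added client were faculty, the multiplier would fall to 136/300 − 0.211 = 0.243. The artefact halves but does not vanish.
- *Several years pooled.* Five years treated as independent clients (5 × 196 = 980) would give 34%, 86% and about 100%. This counts anyone seen in more than one year twice, so I do not rest the point on it.

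**What can and cannot be matched.**

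| Variable | RFWP clients | ISP participants |
|---|---|---|
| Gender | Crude only; confounded by role | Crude only; confounded if role mix differs |
| Ethnicity | Crude only; confounded by role | Not held |
| Age | Year of birth against group means: possible | Bands against group means: rough only |
| Specialty or programme type | Possible within role | Possible if the five groups can be collapsed to match |
| Trainee/faculty mix | Possible from headcounts | Possible from headcounts |

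**The case against.** The strongest reply is that the list is terse and may simply carry the groups in its first line down to the percentages below. That reading is possible, and nothing in the protocol says that only pooled figures will be supplied. Against it, the age and specialty lines repeat the groups, which would be unnecessary if the split carried over. The safest conclusion is that the request is ambiguous and, read literally, pooled.

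It is also fair to say that the protocol fixes no test, that stratification is normally left to the SAP, and that these are largely descriptive questions. This stands as far as the method goes, but stratified analysis needs split reference data. The size of the bias does rest on assumed gaps.

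A reader might infer that the reference data cannot support the representativeness comparisons at all. The protocol does not bear that out. RFWP age, specialty and trainee/faculty mix can be compared, the specialty counts serve the primary-care half of hypothesis 8b, and the crude gender and ethnicity comparisons are confounded rather than impossible.

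Three further inferences also go too far:
- The absence of ISP ethnicity is not a fault of the reference request, which does ask for ethnicity. It follows from the limit on identifiers in the ISP database, and research question 2 does not name ethnicity.
- The "primary" faculty in the request are not shown to differ from the invited 0.5 FTE group, because the term is not defined.
- Leaving Legacy out of Statistical Analyses is a small wording inconsistency, about 90 of 3980 people, and plausibly reflects the end of new Legacy enrolment on 7/1/21.

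**Conclusion.** The point holds in limited form. As written, the request omits the trainee/faculty split for gender and ethnicity, and the protocol's utilisation figures make that omission matter. A crude comparison with a pooled reference carries about 0.48 times the trainee-faculty gap. For assumed gaps of 5, 10 and 20 points, and 40% women among faculty (also assumed), a single year's comparison would falsely reject in about 11%, 28% and 78% of cases instead of 5%. If trainees and faculty have the same percentages, the bias is zero. The protocol does not give those percentages, so the actual size is unknown.

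The ISP gaps are separate and follow from the text alone. The change is worth making because a later analysis cannot recover a split that was not requested.

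**What to change.** - In SOM Summary Data, request counts for gender and for ethnicity by trainee/faculty status and by institution.
- Request age counts in the same categories that the ISP database uses, alongside the group means.
- State that the comparisons for research questions 2 and 8 will be made within trainees and within faculty, or standardised to the trainee/faculty mix. Either removes the role-mix artefact.
- State that ISP representativeness on ethnicity cannot be assessed.
- Make Statistical Analyses agree with SOM Summary Data on Legacy for the years in which its residents were enrolled.

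The cost is a reworded request to the same data analyst and a stratified table. Some small cells, especially ethnicity within the affiliate programmes, may need suppression or merging.
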